10.4.3 Per Protocol (PP) Population

The per protocol (PP) population is defined as all mITT subjects who had no major protocol violations. Subjects will be analyzed based on the treatment that they actually received. The PP population will be used to analyze the primary and key secondary efficacy endpoints.

10.4.4 Safety Analysis Set

The safety analysis set will consist of all subjects enrolled in the study who receive at least one administration of investigational product. The safety population will be used for all safety analyses.

10.5 Primary Efficacy Analysis

This analysis will be performed using the mITT population. This analysis will be assessed for the first headache treated with the investigational product and all headaches treated as well.

10.6 Secondary Efficacy Analyses

No adjustments will be made for multiplicity in the analyses of the secondary efficacy endpoints.

This analysis will be performed using the mITT population. This analysis will be assessed for the first headache treated with the investigational product and all headaches treated as well.

10.7 Exploratory Efficacy Analyses

No adjustments will be made for multiplicity in the analyses of the exploratory efficacy endpoints.

This analysis will be performed using the mITT population. This analysis will be assessed for the first headache treated with the investigational product and all headaches treated as well.

The extent of exposure will be compared between the two treatment groups descriptively for the first headache as well as the all headaches analysis.

10.8 Safety Analysis

All safety analyses will be performed on all enrolled subjects.

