8.1.3 Physical Examination

A full physical exam, including all major body systems and neurological exam, will be performed at the Screening Visit and at the End of Study Visit. Any conditions or symptoms reported after the subject is enrolled will be recorded as an AE on the AE eCRF. This includes new events after nasal CO₂ administration, conditions that become more severe or increase in frequency, any disease-related signs or symptoms present at the Screening Visit (see Section 8.1.2) that have worsened in severity or frequency, as well as any event or finding that the Investigator feels is clinically significant.

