8.1.8 Training

A member of the study site personnel, the trainer, will train enrolled subjects on the following:

- How to complete the headache-related symptom assessments and enter the nasal CO₂ administration details in eDiaries
- How and when to administer the nasal CO₂ using the Directions for Use as a guide
 - This includes using the activated device one time 5 seconds/nostril
- How to enter data (e.g., to medical problems, medications/treatments, etc.) in the eDiary
- When it is acceptable to take rescue medication, if needed
- When the dispenser is operating properly (i.e., makes a hissing sound, which will be demonstrated by the trainer during the Screening Visit) and to contact the site if the dispenser is not operating properly
- Contact site if experiencing any significant AEs and, if after hours, subject should go to the emergency room

It is the responsibility of the study site personnel to ensure that each subject completely understands how to do all of these tasks. This training should be documented in the subject's eSource/eCRF documents.

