8.1.11 Adverse Events

Subjects will be monitored for safety from the time they are enrolled until the End of Study Visit.

Non-serious adverse events (NSAEs) will be collected beginning after the first dose of study medication through the End of Study Visit and will include any change from the subject's condition at Screening.

SAEs will be collected following enrollment and will include any change from the subject's baseline condition at Screening. SAE collection will conclude at End of Study or until resolution of the SAE if it extends beyond the End of Study Visit.

Subjects will be instructed to record in the eDiary any adverse events they experience from the time they are enrolled at the Screening Visit until their End of Study Visit. Any conditions or symptoms reported will be recorded as an AE in the subject's AE eCRF page. Subjects who have an ongoing AE related to study drug and/or study device will be followed until resolution or stabilization of the event.

At the End of Study Visit, subjects will be asked by the Investigator or an appropriate member of the study site personnel about any AEs they have experienced since the previous visit. All AEs recorded by the subject in the eDiary will be discussed and reviewed by the Investigator or an appropriate member of the study site personnel, recorded in the subject's source documents, and on the appropriate eCRF. Subjects will be instructed to contact the study site in the event they experience any significant AEs. At the discretion of the Investigator, the subject may be asked to come to the study site for an Unscheduled Visit. Additional information regarding AEs is provided in Section 9.0.

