9.3 Reporting of Safety Information

9.3.1 Adverse Event Reporting

All AEs, regardless of causality, severity, whether expected or not, must be entered on the AE CRF. Disease-related signs and symptoms that are present at baseline should not be reported as AEs unless they worsen in severity or frequency. Information collected concerning AEs will include the following:

- Name of the event
- Start date
- Stop date or if the event is continuing
- Intensity

- Mild (does not interfere with subject's usual function)
- Moderate (interferes to some extent with the subject's usual function)
- Severe (interferes significantly with subject's usual function)
- Relationship to investigational product (drug, device or both)
- Seriousness of event
- Outcome
- Action taken

Non-serious adverse events will be collected beginning after the first dose of study medication through the End of Study Visit and will include any change from the subject's condition at Screening. All NSAE that are deemed related to study drug and/or study device will be followed until resolution or stabilization of the event. SAEs will be collected following enrollment and will include any change from the subject's baseline condition at Screening. SAE collection will conclude at End of Study or until resolution of the SAE if it extends beyond the End of Study Visit.

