10.8.1 Adverse Events

Adverse events (AEs) will be monitored throughout the study. All reported AEs will be documented on the appropriate eCRF. All similar AEs will be combined into one category and the frequency of all AEs occurring above 5% will be reported.

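### Sections 10.4.4 and 10.8 give all safety analyses to two different populations; and, if its base is subjects, the 5% cut in 10.8.1 drops one-subject AE categories from the summary at 20 or more subjects

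*Combined protocol and SAP*

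**What the plan says.** **Population.** Section 10.4.4 defines the safety analysis set as "all subjects enrolled in the study who receive at least one administration of investigational product" and assigns it to every safety analysis. Section 10.8 then says "All safety analyses will be performed on all enrolled subjects". That is the membership of the ITT population in 10.4.1.

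**Start of AE recording.** Section 8.1.11 says "Non-serious adverse events (NSAEs) will be collected beginning after the first dose of study medication", and 9.3.1 agrees: "Non-serious adverse events will be collected beginning after the first dose of study medication through the End of Study Visit". But 8.1.3 says "Any conditions or symptoms reported after the subject is enrolled will be recorded as an AE on the AE eCRF", and the eDiary instruction in 8.1.11 has subjects record "any adverse events they experience from the time they are enrolled at the Screening Visit until their End of Study Visit". For serious AEs (SAEs), 8.1.11 and 9.3.1 both begin at enrolment.

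**Training use.** The training in 8.1.8 is for enrolled subjects. On the device it says "This includes using the activated device one time 5 seconds/nostril". The schedule in 8.2 places training at Screening. The plan does not say whether this counts as an administration under 10.4.4.

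**Reporting cut.** Section 10.8.1 pools similar AEs and says "the frequency of all AEs occurring above 5% will be reported". It names no denominator and makes no exception for SAEs or AEs leading to withdrawal. The statistical paragraph of the synopsis promises AE frequency with no cut. Section 10.8.4 provides listings of examination results and other safety observations, without naming AEs.

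**The concern.** Safety is part of the primary objective (4.1), and the AE table is its main output. Two sections each claim all safety analyses and name different sets, so whoever programs the table must choose, in an open-label study whose data are under continuing review (5.4, 10.9). The choice affects both the denominator and which events are counted.

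The plan foresees enrolled subjects who never treat. Enrolment is at Screening (7.1.1), treatment may begin up to 12 weeks later (5.0), and 6.3 lists the absence of a cluster episode within 84 days as a reason for removal. Section 6.3 also lets early withdrawals be replaced, so the number enrolled can exceed the number treated.

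The 5% cut is a separate matter. In a trial of about 25 subjects, a single case of an AE is useful information, and a percentage threshold can remove it from the only AE summary that section 10 describes.

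**Working it through.** The plan gives no calculation on this point, so there is no figure to reproduce. Inputs from the documents are 25 subjects (synopsis, 5.0) and a cut strictly above 5% (10.8.1). The numbers dosed, the numbers affected and the true AE risks below are assumptions.

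**1. SAEs.** Collection starts at enrolment. Take an enrolled subject who has an SAE and never treats an attack. Under 10.8 the SAE is in the table. Under 10.4.4 it is not, unless the training use made that subject a member of the set. This needs no assumption about non-serious AEs.

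**2. Non-serious AEs counted only after the first dose (8.1.11, 9.3.1).** Never-dosed subjects add to the 10.8 denominator and cannot add to the numerator. The rate under 10.8 equals the rate under 10.4.4 times dosed/enrolled. With 5 affected subjects:

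| Dosed / enrolled (assumed) | Factor | 10.4.4 | 10.8 |
|---|---|---|---|
| 25 / 25 | 1.00 | 5/25 = 20.0% | 5/25 = 20.0% |
| 25 / 30 | 0.83 | 5/25 = 20.0% | 5/30 = 16.7% |
| 20 / 25 | 0.80 | 5/20 = 25.0% | 5/25 = 20.0% |

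**3. AEs recorded from enrolment (8.1.3, eDiary instruction).** Never-dosed subjects can now contribute events. With 20 dosed, 5 never dosed and 5 affected among the dosed (25.0%), one affected never-dosed subject gives (5+1)/25 = 24.0%, and two give (5+2)/25 = 28.0%. The direction can reverse.

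**4. Training use counted as an administration.** The two sets then nearly coincide. But trained, never-treated subjects would sit in the safety set itself, and if non-serious AEs still start only at the first treatment dose, the dilution in step 2 occurs inside 10.4.4 as well. Membership and the start of counting therefore need the same definition.

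**5. The cut, read as percent of subjects.** A category seen in k of N subjects is reported only if k/N > 0.05, that is, 20k > N. For k = 1:

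- N = 19: 1/19 = 5.26%, reported.
- N = 20: 1/20 = 5.00%, not above 5%, omitted.
- N = 25: 1/25 = 4.00%, omitted. The smallest rate shown is 2/25 = 8.0%.

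So the condition is exactly 20 or more subjects. With X ~ Binomial(25, p), P(X=1) = 25p(1−p)^24 and P(X≥1) = 1 − (1−p)^25:

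| True risk p (assumed) | P(X=1) | P(X≥1) | P(omitted, given it occurs) |
|---|---|---|---|
| 2% | 0.308 | 0.397 | 0.776 |
| 5% | 0.365 | 0.723 | 0.505 |
| 10% | 0.199 | 0.928 | 0.215 |

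**6. Interaction.** Assume 25 enrolled and 19 dosed. A one-subject category is 1/25 = 4.0% and omitted under 10.8, but 1/19 = 5.3% and reported under 10.4.4.

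**The case against.** The population conflict may be largely verbal. Section 10.4.4 asks for an administration, not a dose. Section 7.1.1 uses administration for each nostril's application and dose for the pair, and the mITT definition in 10.4.2 asks for a dose. On that wording the training use at Screening could put nearly every enrolled subject in the safety set. The sets also nearly coincide if every enrolled subject treats; 5.3 lets untreated subjects stay a further 12 weeks at the investigator's discretion. This stands as a limit on the size of the effect. It does not remove the contradiction, because the plan never says that training use counts.

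On the cut, 10.8.1 does not say what the 5% is a percentage of. Treated attacks or reported events are possible bases, and step 5 does not carry over to them. The section also does not forbid reporting rarer AEs, and the listings in 10.8.4 may be meant to include them. So omission is conditional on the subject base, and part of the objection to a threshold is preference. What remains is that the plan nowhere commits to tabulating or listing SAEs, AEs leading to withdrawal, or one-subject categories.

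A reader might infer that 10.8 necessarily understates AE rates. The documents do not support that: 8.1.3 and the eDiary instruction allow events in never-dosed subjects, and step 3 shows a rise as well as a fall. A reader might also infer that safety data are lost. They are not: every AE goes on the eCRF (9.1, 10.8.1), and SAEs are reported within 24 hours (9.3.2).

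**Conclusion.** The contradiction between 10.4.4 and 10.8 is on the page and needs correcting. Its clearest effect is on SAEs in never-dosed subjects, which one section counts and the other does not, unless training use is an administration. For non-serious AEs the effect runs from none (all enrolled subjects treat) to a factor of 0.80 in the assumed case of 20 dosed of 25. The direction is open until the start of recording is settled.

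The 5% cut is a cheap improvement rather than an error. If the base is subjects, at the planned 25 it works as a rule of at least two subjects.

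The point is minor. This is a single-arm, open-label pilot, no stated decision rule uses an AE percentage, and only the planned summary is affected. The splits and true risks are assumptions; the contradiction and the threshold of 20 subjects do not depend on them.

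**What to change.** - **10.8:** replace the reference to all enrolled subjects with the safety analysis set.
- **10.4.4:** state whether training use counts as an administration. Use the same first exposure for membership of the set and for the start of non-serious AE counting, and reconcile 8.1.3, both statements in 8.1.11, and 9.3.1 with it.
- **SAEs before any exposure:** list SAEs in never-exposed subjects separately, so that restricting the set does not drop them.
- **10.8.1:** delete the 5% cut. Tabulate every AE category as number and percentage of subjects in the safety analysis set, and list all SAEs and all AEs leading to withdrawal.

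The cost is a few sentences and a slightly longer AE table. AE percentages may come out higher than under 10.8: by 30/25 = 1.20 or 25/20 = 1.25 in the two assumed splits if non-serious AEs count only after the first dose, and almost unchanged if all enrolled subjects treat. The wording should be settled before AE data are summarised.

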10.8.1 Adverse Events

Adverse events (AEs) will be monitored throughout the study. All reported AEs will be documented on the appropriate eCRF. All similar AEs will be combined into one category and the frequency of all AEs occurring above 5% will be reported.

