This is an open label, investigator-sponsored, pilot study. Subjects agreeing to participate in the study and meeting the eligibility criteria assessed at the screening visit will be enrolled in the study. The length of time between screening and treatment will last between 0 days to a maximum of 12 weeks. Subjects who enter the screening phase during a cluster headache episode and meet the study eligibility criteria can immediately enter the treatment phase and may opt to treat their cluster headache episode in the clinic. Subjects who are not in a cluster headache episode, who meet initial screening eligibility criteria, can remain in the screening phase for up to 12 weeks until their next cluster episode begins. Upon initiation of a cluster headache episode, subjects will enter the treatment period. Subjects will be trained on the proper use of the hand-held dispenser containing CO₂ calibrated to deliver 0.5 standard liters per minute (SLPM). This dispenser will be provided for use in the clinic or home. Subjects will be instructed to use the nasal CO₂ dispenser, 10 seconds/nostril, as needed up to 6 times to treat one attack. Each dose must be separated by 3-5 minutes. Subjects should treat only one attack in a 24-hour period. Subjects may treat up to three cluster headache attacks during the treatment phase of this study. One hour after the first dose, subjects can choose to treat with investigator-approved rescue medication. Subjects will be asked to complete an online diary after the completion of the dosing. Diary assessments will collect pain severity (0=none, 1=mild, 2=moderate, 3=severe), symptoms (such as tearing, nasal congestion, and running nose), nasal CO₂ usage, acute medication usage, satisfaction of treatment, number of cluster attacks, and unusual symptoms. Subjects will be contacted by phone within 3 days of the first use of the nasal CO₂ dispenser to assess adverse events (AEs) and medication usage. A total of 25 subjects will enter the treatment period and be instructed to treat up to 3 cluster headaches with nasal CO₂. Within 7 days of treating their last cluster headache episode, subjects will return for an end of study visit.

Number of Subjects:	Up to 25 subjects enrolled and treating up to 3 cluster headaches in one cluster headache period.

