6.3 Subject Withdrawal

Subjects are free to withdraw consent and discontinue participation in the study at any time without prejudice to further treatment. A subject's participation in the study may be discontinued at any time at the discretion of the Investigator. Justifiable reasons for the removal of a subject from the study include but are not limited to:

- The subject's request
- The subject is non-compliant in the opinion of the Investigator
- The subject resumes or initiates other medication not permitted in this study
- The subject experiences an adverse event which, regardless of seriousness or severity, prohibits further participation in the study
- The subject does not have a cluster headache episode within 84 days (12 weeks) after Enrollment
- The subject becomes pregnant, at which time she is to inform the study site personnel

Enrolled subjects who withdraw from the study must return to the study site for the End of Study Visit. If during this visit, the Investigator determines that the subject has an ongoing study drug-related or study device-related adverse event, the subject will be followed until resolution or stabilization.

The reasons for withdrawal must be documented accordingly in the subject's eSource documents/eCRF. Subjects who withdraw early from the study may be replaced.

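### The 5% cut in 10.8.1 can omit a severe adverse event seen in one subject, no planned summary uses the intensity and relationship collected, and the safety denominator is stated two ways

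*Combined protocol and SAP*

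**What the plan says.** Section 10.8.1 states: "All similar AEs will be combined into one category and the frequency of all AEs occurring above 5% will be reported". It does not say whether frequency counts subjects, events or treated attacks. The Statistical Methods entry of the synopsis plans descriptive AE frequency and sets no 5% limit.

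Section 9.3.1 collects, for each AE, intensity (mild, moderate, severe), "Relationship to investigational product (drug, device or both"), seriousness, outcome and action taken. Section 9.2.2 defines suspected adverse reactions. No part of Section 10 tabulates AEs by any of these. Section 10.8.4 sends examination results and other safety observations to listings without naming AEs.

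Two safety sets are given. Section 10.8 says: "All safety analyses will be performed on all enrolled subjects". Section 10.4.4 defines a set of enrolled subjects with at least one administration and adds: "The safety population will be used for all safety analyses".

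The size is given in the synopsis as "Up to 25 subjects enrolled and treating up to 3 cluster headaches". Among the reasons for withdrawal, Section 6.3 lists "The subject does not have a cluster headache episode within 84 days (12 weeks) after Enrollment", so some enrolled subjects may never treat an attack. Section 8.1.8 says of the training on administering the gas: "This includes using the activated device one time 5 seconds/nostril".

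**The concern.** Safety is half of the primary objective (4.1). In a trial this small, a percentage cut acts as a rule about one subject versus two. Followed literally, it leaves a severe but non-serious reaction in a single subject out of the AE summary.

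The anticipated harms in Section 3.4 start with administration-site reactions. For these the useful question is how bad they are, because some occurrence is expected. A merged frequency cannot answer that.

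The choice of denominator also matters. Non-serious AEs are formally collected only after the first dose (8.1.11, 9.3.1). Enrolled subjects who were never dosed therefore add to the denominator and almost nothing to the numerator, which dilutes every rate.

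**Working it through.** The documents derive no figure here; the 5% is simply stated. The inputs are the strict cut of above 5% (10.8.1) and N = 25 (synopsis; Section 5.0 also plans 25 entering treatment). Counting by subject is an assumption.

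**1. What the cut means at N = 25.**
- One subject: 1/25 = 4.0% (exact 95% CI 0.1% to 20.4%), not reported.
- Two subjects: 2/25 = 8.0% (1.0% to 26.0%), reported.

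**2. Dependence on N.** One case is reported only if 1/N > 0.05, that is N < 20.
- 1/19 = 5.3%: reported.
- 1/20 = 5.0%: not above 5%, so omitted.
- 1/30 = 3.3%: omitted. Replacing withdrawals (6.3), which can raise N, does not help.

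**3. How often an event is seen but omitted.** For an assumed true per-subject rate p, P(exactly one) = 25p(1−p)^24 and P(none) = (1−p)^25.

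| Assumed p | None | Exactly one (omitted) | Two or more (reported) |
|---|---|---|---|
| 2% | 60.3% | 30.8% | 8.9% |
| 5% | 27.7% | 36.5% | 35.8% |
| 10% | 7.2% | 19.9% | 72.9% |

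**4. If something else is counted.**
- Per treated attack, with at most 25 × 3 = 75 attacks: 5% is 3.75, so four affected attacks would be needed.
- Per AE report, with an assumed 15 reports: 1/15 = 6.7%, so a single event would be shown.

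The result for a single case therefore depends on a unit that the plan leaves open.

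**5. Common reactions.** Section 3.3.4.5 gives nasal discomfort in 36.8% of CO₂ subjects in the earlier migraine study C113. If that rate applied here (an assumption: different disease, up to four doses there against six here), the chance of one or no affected subject in 25 is 0.632^25 + 25 × 0.368 × 0.632^24 ≈ 0.0002. This category would be reported. What it would lack is the split by intensity.

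**6. Denominator conflict.**
- Assumed 25 enrolled and 19 in the 10.4.4 set: the same single case is 4.0% under 10.8 (omitted) and 5.3% under 10.4.4 (reported).
- Assumed 30 enrolled and 25 in the 10.4.4 set: one case is 3.3% or 4.0%, omitted either way; two cases are 6.7% or 8.0%, reported either way. Only the size of the rate changes.
- If training use counts as an administration, nearly every enrolled subject is in the 10.4.4 set and the two denominators almost coincide.

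**The case against.** The strongest reply is that this is an uncontrolled pilot in which every AE goes onto the eCRF, and that 10.8.1 says what will be reported without forbidding a fuller listing. Serious events go to the manufacturer within 24 hours and to the IRB (9.3.2). Section 10.8.4 could be stretched to cover individual AEs, and a clinically significant nasal finding at an examination would appear in its listings with no frequency limit. About 820 migraine and 975 rhinitis subjects took part in earlier trials, so this is not first exposure to the product. Baseline symptoms are also sensibly handled: "Disease-related signs and symptoms that are present at baseline should not be reported as AEs unless they worsen in severity or frequency". Much of this stands, but none of it commits the plan to a summary by intensity or relationship, and expedited reporting does not reach severe non-serious events.

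Several stronger readings are tempting and should not be drawn:
- *Severe events would go unrecorded.* They would not. The gap lies in the planned summary, not in collection.
- *The 5% cut hides administration-site reactions.* It very probably does not, as step 5 shows. The cut affects rarer events.
- *The whole document imposes the cut.* The synopsis does not.
- *Confidence intervals are missing.* Section 10.1 already requires 95% intervals with all analyses.
- *The eCRF lacks a causality rating.* The form is not in the documents, and 9.3.2 (for SAEs) and Section 14.0 call for causality to be assessed.
- *The upper limit of about 20% is caused by the rule.* It mostly reflects the sample size; 0/25 already has an exact upper limit of 1 − 0.025^(1/25) = 13.7%.

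Nor can any reporting rule recover an event that does not occur, which is the likeliest outcome at a true rate of 2%.

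**Conclusion.** The point holds in three parts of unequal firmness.

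- **No summary by intensity or relationship.** This depends on no assumption about N or counting unit, and it is the part that affects the common reactions.
- **The 5% cut.** Counted by subject, it omits any one-subject category, whatever its severity, at every N of 20 or more. The chances of 20% to 37% in step 3 rest on assumed true rates and on N = 25.
- **The safety set.** Sections 10.8 and 10.4.4 contradict each other as written. The practical effect runs from almost nothing, if training use counts as an administration, to deciding whether a single case is shown. The documents do not say where in that range the trial falls.

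This should be changed: it concerns a stated rule applied to part of the primary objective, and the correction is cheap. It does not touch the efficacy analyses, dosing or sample size.

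**What to change.** 1. In 10.8.1, state that frequency means the number and percentage of subjects, with the 10.4.4 safety set as denominator. Correct 10.8 to match, and state whether the training use in 8.1.8 counts as an administration.
2. Report all AE categories by maximum intensity and by investigator-assessed relationship. Alternatively, keep the 5% cut for the summary table only and exempt severe AEs, SAEs, suspected adverse reactions (9.2.2) and AEs leading to withdrawal.
3. List every severe or serious AE whatever its frequency. Because SAEs are collected from enrollment, run this listing over all enrolled subjects.

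The cost is a few lines of SAP text, one extra descriptive table and one listing. Intensity, relationship, seriousness and action taken are already listed fields in 9.3.1. Cells will be small, so the table should be read descriptively, and relationship should be read as an open-label investigator judgement.
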